### **3.2.4.3 Adverse Events and Clinical Complications**

Adverse Events (AEs), including complications associated with an untoward medical occurrence, from the start of the index procedure until completion of the 12 month follow-up will be coded using the MedDRA system and summarized with frequencies. Serious adverse events (SAEs), device- or procedure-related AEs, unanticipated adverse device effects (UADEs) and deaths will be presented.

AEs will be presented for the following study periods: 1) peri-procedure – i.e., from the start of the procedure until 24 hours post-procedure; and, 2) through 12 month follow-up – i.e., from 24 hours post-procedure through the 12 month visit or premature termination.

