#### ***Assessment and subject interview***

- Vital Signs (Blood pressure, Heart Rate, and Respirations)
  - Immediately Post-Treatment
  - Hospital discharge
- Relevant Concomitant Medications (daily): indicate all antithrombotics (including anti-platelets, anticoagulants, and fibrinolytics), and inhibitors of ADP-induced platelet aggregation medications that were administered after 24 hours post-procedure through hospital discharge.
- Neurological assessment and evaluations performed by qualified personnel at 12-36 hours after end of procedure (removal of the guiding catheter from the subject). Included as part of this examination are the NIH Stroke Scale Score, Modified Rankin Scale, clinical neurological evaluation, and if applicable, the Hunt and Hess Scale (HHS) for subarachnoid hemorrhage

- Event assessment (daily) as applicable (i.e. adverse events, protocol deviations, device malfunction/product complaint).

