## **POST-PROCEDURE**

After the end of the index procedure (removal of the guiding catheter from the subject)

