10.1 General Conventions

According to the Close Out plan, only descriptive statistics and listings will be presented, no inferential statistics will be performed for the primary and secondary endpoint. Descriptive statistics for continuous variables will include the number of subjects, mean, standard deviation, median, minimum and maximum. Descriptive statistics for dichotomous/categorical variables will include the number and percentage of subjects. All summary tables will be presented overall. Unless specified otherwise, percentages are based on non-missing values, excluding missing data and subjects who early discontinued.

- Baseline

Baseline is defined as the last non-missing measurement prior to the index procedure.

- Study Day

Unless specified otherwise, Study Day will be calculated as the difference between the event date and the date of index procedure, i.e., event date - date of index procedure. The day of index procedure is considered as Day 0.

- Date conversion

For the purposes of statistical analyses, a month is considered equivalent to 30 days and a year is considered equivalent to 360 days.

- SAS version

All statistical analyses will be performed using SAS®, Version 9.2 or later, unless otherwise noted.

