10.4.2.2 Secondary Safety Endpoints

- Rate of new neurological deficits as per mRS

The number and percentage of subjects with new neurological deficits, not related to stroke or death, will be summarized at baseline (pre-procedure) and follow-up visits, e.g., 30 days, 6 and 12 months post-procedure. Subjects who died prior to an evaluation will have an mRS score of 6 imputed at that timepoint for analysis purpose.

- NIHSS total score

The NIHSS total score and its change from baseline will be summarized at baseline (pre-procedure) and follow-up visits (6 months and 12 months post-procedure). In addition, the number and percentage of subjects who show a worsening from baseline (an increase of 4 points or more) will also be presented. Only the observed scores will be included in summaries.

- Adverse Events and Clinical Complications

AEs from the start of the index procedure until completion of the 12-Month Follow-up will be coded using the latest version of Medical Dictionary for Regulatory Activities (MedDRA) into system organ class (SOC) and preferred terms (PTs). The number of events, the number and percentage of subjects with events and event rates by SOC and PT will be summarized for the following:

- Any AEs
- Study device or procedure related AEs
- Any serious AEs (SAEs)
- Unanticipated AEs
- AEs leading to death

AEs related to device/procedure are defined as those with the relationship of definitely, probably or possibility related. AEs with miss relationship will not be imputed. Subjects with multiple relationships on the same AE will be reported by the events of the highest relationship. Only the relationship as determined by CEC will be used in the safety analysis.

In addition, device or procedure related AEs will be presented overall and by study period as follows:

Table 2: AEs by Study Period

Study Period	Lower Bound of AE Start Date	Upper bound of AE Start Date
Peri-procedure	from the beginning of the procedure	Until 24 hours post-procedure (Day 0)
12-Month Follow-up	After 24 hours post-procedure (i.e., from Day 1)	Until the date of: 
○ early discontinuation in the study; or

Study Period	Lower Bound of AE Start Date	Upper bound of AE Start Date
		
 ○ the upper bound of the 12-Month analysis window (i.e., Day 450)

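### SAP Table 2 bounds the peri-procedure AE period in two ways that disagree (24 elapsed hours and calendar Day 0), and it splits only related AEs where the protocol splits all AEs

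*SAP*

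**What the plan says.** Protocol 3.2.4.3, repeated in the Overview and in section 9.6, presents AEs in two periods. The first runs "from the start of the procedure until 24 hours post-procedure"; the second runs from that point to the 12-month visit or early termination. Neither is limited to related events. Appendix 1 defines post-procedure as "After the end of the index procedure (removal of the guiding catheter from the subject"), which is a clock time.

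SAP 10.4.2.2 introduces its Table 2 with "In addition, device or procedure related AEs will be presented overall and by study period as follows". The upper bound of the peri-procedure period is "Until 24 hours post-procedure (Day 0"), and the lower bound of the follow-up period is "After 24 hours post-procedure (i.e., from Day 1"). Both columns are headed as bounds on the AE start date.

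SAP 10.1 supplies the meaning of Day 0 and Day 1: "Study Day will be calculated as the difference between the event date and the date of index procedure", and "The day of index procedure is considered as Day 0".

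**The concern.** Table 2 states one boundary in hours and glosses it with another in calendar days. An event at 02:00 on the morning after a procedure that ended at 14:00 is 12 hours post-procedure. By the hours it is peri-procedure; by Study Day it is follow-up. Two programmers could build different tables from the same SAP.

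AEs by period belong to a protocol secondary safety endpoint, and the table's purpose is to separate the immediate hazard of stenting and coiling from later events. If the Day rule is used, related events from the first night and following morning move to follow-up. The peri-procedure rate is then too low and the follow-up rate too high.

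The first scheduled neurological examination adds to this. Protocol 6.3.3 places it in the window "Neurological assessment and evaluations performed by qualified personnel at 12-36 hours after end of procedure", so a deficit found and dated at that visit may fall within 24 hours but on Day 1.

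The scope is a separate matter. The protocol splits AEs of any relationship, while the SAP splits only those related to device or procedure.

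**Working it through.** The plan gives no figure to reproduce, so the check applies the SAP's own day rule to the protocol's 24-hour window.

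**Inputs**
- Window: 24 hours from guiding catheter removal (Protocol 3.2.4.3 and Appendix 1).
- Study Day: event date minus procedure date, with the procedure date as Day 0 (SAP 10.1).
- Clock hour of removal, t: not in the documents. It is assumed, shown over a range, and taken to fall on the procedure date.

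**Hours of the window on each day**

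Day 0 holds 24 − t hours and Day 1 holds the other t hours, a time share of t/24.

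| Removal | On Day 0 | On Day 1 | Share of window on Day 1 |
|---|---|---|---|
| 10:00 | 14 h | 10 h | 10/24 = 41.7% |
| 14:00 | 10 h | 14 h | 14/24 = 58.3% |
| 18:00 | 6 h | 18 h | 18/24 = 75.0% |

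The two boundaries coincide only for removal at midnight.

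**Time is not events.** The shares equal event shares only if onsets after removal are evenly spread. If onsets cluster early, fewer move. With an assumed 6-hour half-life truncated at 24 hours, the share on Day 1 is (2^(−(24−t)/6) − 2^(−4)) / (1 − 2^(−4)), which gives 14.5%, 26.9% and 46.7% for the three times. Events during the procedure normally stay on Day 0 and lie outside both calculations.

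**Examination window.** Day 1 begins 24 − t hours after removal. For t of 12 or more, this is at most 12 hours, so the whole 12–24 hour part of the examination window lies on Day 1. For t = 10 it begins at 14 hours, so 10 of those 12 hours (83%) do. The 24–36 hour part is follow-up under the protocol's rule as well.

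**Which rule is likely to be programmed.** The columns bound a start date, the second row explains its hours as Day 1 onward, and Study Day uses dates only. The SAP's rule for incomplete onset covers a missing day, month or year but not a missing time. By contrast, SAP Table 1 states its immediate post-procedure and discharge windows in hours with no day gloss.

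**Scope.** SAP 10.4.2.2 summarizes all AEs, related AEs, SAEs, unanticipated AEs and AEs leading to death. Only related AEs are then split by period.

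**The case against.** The strongest reply is that Table 2 keeps the 24-hour wording in both rows. The documents do not show whether AE start time is collected: the eCRF details are in the Manual of Operations (Protocol 11.3) and the table shells are a separate document (SAP section 11). With times available, a programmer could follow the hours. This stands. A reader might infer that these events will certainly be misclassified, but the text supports only that the boundaries disagree and that the day rule is the likelier reading.

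A reader might also infer that every error runs in one direction. For events after femoral access it does. However, AE reporting begins at consent (Protocol 10.5.2), and a pure date rule cannot separate Day 0 events before access from those after it. This should seldom matter for related events.

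It is also tempting to turn the time shares into rates using the European registry in Protocol 1.3.4. That registry reports related events before hospital discharge, with no 24-hour count and no clock times. Any rate drawn from it would rest on assumptions the documents do not supply.

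The examination example applies only if the visit falls at 12–24 hours and the event is dated to the visit rather than to symptom onset.

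Finally, the trial stopped for low enrollment, the analysis is descriptive, and no AE drops out of the report. That limits the consequence but does not reconcile the two boundaries. On scope, a reason may lie in the Close Out Plan, which is not available here. The SAP gives reasons for dropping the hypothesis tests and the interim analysis, but none for this change, and a descriptive split does not depend on reaching the planned sample size.

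**Conclusion.** The point holds in limited form. Table 2 contains two incompatible boundaries, and its calendar boundary contradicts the protocol for any event that starts after midnight but within 24 hours of catheter removal. If that boundary is programmed, which is likely but not certain, the peri-procedure rate of related AEs is understated. For assumed removal between 10:00 and 18:00, 10 to 18 of the 24 post-procedure hours are assigned to follow-up. The number of events affected cannot be estimated from the documents. The restriction to related AEs is a separate, unexplained departure from the protocol.

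The effect is confined to one descriptive secondary safety table. It should be corrected before programming, but it does not threaten the trial's main results.

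**What to change.** - Delete both day glosses from Table 2. Define peri-procedure as an AE start date and time from femoral access to 24 hours after guiding catheter removal.
- Where the start time is not available, count AEs dated Day 1 as peri-procedure and footnote the overshoot. This fallback reaches up to 48 − t hours after removal: 38, 34 or 30 hours for removal at 10:00, 14:00 or 18:00. It therefore captures some events that belong to follow-up.
- Present the split for all AEs, as the protocol states, alongside related AEs.

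The cost is a wording change, one derivation rule and a further run of the same table. The fallback needs no new data.

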### **10.5.2 Adverse Event Reporting for Entered Subjects**

The adverse event reporting period for this study begins at the time the study informed consent is signed and ends at the twenty-four month follow-up unless noted otherwise in Section 11.3. Adverse events that occur in subjects during the adverse event reporting period must be entered into the eCRF database. All required treatments and outcomes of the adverse event must be recorded.

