If the AE onset day is missing but the month and year is available, then the missing day will be imputed to be Day 1 of that month as a conservative approach. As an example, if the AE has an onset date of July of 2016, with an unknown day, the imputed onset day would be 01JUL2016. If the month and/or year is unknown, then, the AE will be categorized as unknown.

- Reduced TICI Flow

The number and percentage of subjects with a reduced TICI flow (TICI score of 0 or 1) at the target vessel during the index procedure will be summarized. Subjects with missing data on this endpoint will be excluded from analysis.

- Bleeding complications

The number and percentage of subjects who experience a procedure-related hemorrhagic event which requires any of the following will be summarized:

- Blood transfusion
- Surgical intervention
- New hospitalizations
- Lengthening of hospital stay for the index procedure
- In-stent stenosis

The number and percentage of in-stent stenosis at immediately post-procedure (acute), and up to and including 6-Month Follow-up (excluding acute events) will be summarized in the same way the primary safety endpoint (in-stent stenosis) at 12-Month Follow-up.

For subjects with acute in-stent stenosis, the number and percentage of subjects who have parent vessel stenosis caused by vasospasm, and whether vasospasm was responsive to medication will be summarized based on the assessment from the Independent Core Laboratory.

- Thrombosis

The number and percentage of subjects with thrombosis up to and including 6 months and 12 months post-procedure will be summarized based on the assessment from the Independent Core Laboratory. Subjects with missing data on thrombosis will be excluded from analysis.

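### Adverse event dating in the SAP: the protocol's 24-hour peri-procedure window becomes Day 0 only, and a missing onset day can be set to before the procedure

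*SAP*

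**What the plan says.** Protocol 3.2.4.3 defines the peri-procedure period for adverse events as running "from the start of the procedure until 24 hours post-procedure"; the protocol overview and 9.6 say the same. Protocol 6.2.4 ends the procedure at removal of the guiding catheter.

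SAP 10.1 defines Study Day as event date minus procedure date: "The day of index procedure is considered as Day 0". SAP 10.4.2.2 limits the period split to related events: "device or procedure related AEs will be presented overall and by study period as follows". In Table 2 the peri-procedure period runs "Until 24 hours post-procedure (Day 0", and the follow-up period starts "After 24 hours post-procedure (i.e., from Day 1" and ends at early discontinuation or Day 450.

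For a missing onset day with month and year known, "then the missing day will be imputed to be Day 1 of that month as a conservative approach". The SAP's example turns July 2016 into 01JUL2016 without reference to the procedure date. The only other partial-date rule makes the event unknown when month or year is missing.

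The overall summaries have their own start point: "AEs from the start of the index procedure until completion of the 12-Month Follow-up will be coded". Collection starts earlier, under Protocol 10.5.2: "The adverse event reporting period for this study begins at the time the study informed consent is signed". SAP 10.4.4 lists later events and glosses the cut-off as after Day 451.

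**The concern.** Two rules that assign events to periods do not do what they are meant to do.

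First, the imputation rule is called conservative. For onset in a later month that is fair, because the event moves towards the procedure. For onset in the procedure month it works the other way: an event that followed the procedure can be dated before it. Because events are collected from consent, such a record can resemble a genuine pre-procedure event. It drops out of both Table 2 periods. Read literally, it also falls outside the overall summaries that begin at the procedure. The SAP does not say whether the imputed date decides entry to those.

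Second, Table 2 states the protocol's 24 hours in words and then gives day numbers that mean something shorter. The explicit day numbers are what a programmer would most likely code. The error runs one way: it can only lower the count of related events in the peri-procedure period.

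The split of events into peri-procedure and follow-up is a safety display that the protocol specifies. With hypothesis testing dropped, the descriptive tables are what the report will show.

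**Working it through.** **1. Where the 24-hour mark falls.** Inputs: Study Day from SAP 10.1; end of procedure from Protocol 6.2.4. Let the procedure end at clock hour *h* on Day 0. The 24-hour mark is then hour *h* on the next calendar date, which is Study Day 1. End times from 00:30 to 20:00 were tried, and counting from the start of the procedure was tried as well; the mark was on Day 1 every time. Table 2's equation of 24 hours with Day 0 is therefore not reproduced.

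Of the 24 hours after the end, *h* hours lie on Day 1. If the whole of Day 1 were counted as peri-procedure instead, 24 − *h* hours beyond the limit would be included. The documents give no procedure times, so *h* is an assumption:

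| Procedure ends | Hours within 24 h but on Day 1 | Hours of Day 1 beyond 24 h |
|---|---|---|
| 09:00 | 9 | 15 |
| 12:00 | 12 | 12 |
| 16:00 | 16 | 8 |

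These are clock hours, not shares of events. Protocol 6.3.3 schedules a neurological examination 12 to 36 hours after the procedure. For a procedure ending at noon or later, the whole 12-to-24-hour part of that window lies on Day 1.

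**2. Imputed onset date.** The SAP's example (July 2016 becomes 01JUL2016) follows from its rule. Add a procedure on 15 July 2016: 1 July minus 15 July = Day -14, before the lower bound of Table 2. With the procedure date as the earliest allowed value, it becomes Day 0.

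For a procedure on day *d* of the month and onset in that month, the imputed Study Day is 1 − *d*, which is negative unless *d* = 1. Take every date in 2016 to 2019 as an equally likely procedure date (an assumption; no procedure dates are given):

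- Dates not on the 1st: 1,461 − 48 = 1,413, and 1,413/1,461 = 96.7%.
- The median of *d* is 16 and the maximum 31, so the imputed Study Day has median -15 and minimum -30.

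Next, cross each procedure date with each possible true onset day, all equally likely, and count the pairs where the 1st of the onset month precedes the procedure. In a month of *L* days, with *K* onset days in the window, the count is the sum of min(*K*, *r*) for *r* = 1 to *L* − 1. Over the 48 months:

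| True onset | Pairs dated before procedure | All pairs | Share |
|---|---|---|---|
| Day 0–1 | 2,778 | 1,461 × 2 = 2,922 | 95.1% |
| Day 0–7 | 9,960 | 1,461 × 8 = 11,688 | 85.2% |
| Day 0–30 | 21,520 | 1,461 × 31 = 45,291 | 47.5% |
| Day 0–450 | 21,520 | 1,461 × 451 = 658,911 | 3.3% |

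These shares apply only to events whose onset day is unknown. The documents do not give the number of such events.

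**3. Day 451.** Table 2 stops at Day 450 and the listing's gloss starts after Day 451, so read by the day numbers an event on Day 451 is in neither.

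**The case against.** The best case against the point is that little depends on it. The study stopped early for low enrolment and only descriptive statistics are planned. Stroke and death come from adjudicated data and stenosis from the core laboratory. Events are assessed daily in hospital, so an unknown onset day should be rarest where the 95.1% and 85.2% apply; over the whole window the figure is 3.3%, and the number of affected events could be zero. All of this stands and limits the size of the point.

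It can also be said that the imputation rule follows directly after Table 2 and reads as a rule for assigning a period. On that reading no event leaves the overall tables. This is a fair reading, and loss from those tables is not shown; the SAP should settle it. A related event dated before the device was used would also look odd to an attentive reader, and the table and listing shells are in a separate document. But nothing in the SAP text tells the programmer what to do with such a record.

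For Table 2, the cell does keep the words for 24 hours, and if onset time is collected those words can be applied directly. If it is not, any split by calendar day is approximate. For procedures ending before noon, Day 0 alone misplaces fewer clock hours than Day 0–1 would. That counts against a plain Day 0–1 label and in favour of a separate Day 1 row. It does not make Day 0 equal to 24 hours.

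Finally, the sentence about the later listing refers to events past the upper bound of the 12-month period, and those words cover Day 451. Only the gloss is off by one, so this part is editorial.

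**Conclusion.** The concern holds. As written, the SAP contradicts the protocol's 24-hour definition and its own wording. Its partial-date rule puts an event from the procedure month before the procedure for any procedure not on the 1st of the month.

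The certain consequences are narrow. A related event within 24 hours but on the next date gets the wrong period label, though it stays in the overall tables. A related event from the procedure month with unknown day is dated outside both Table 2 periods. Whether the second kind also leaves the overall summaries cannot be decided from the documents.

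No count of affected events can be given. The hours rest on assumed procedure end times, and the shares on uniform procedure and onset dates. No hypothesis test and no primary safety endpoint is affected. The change should be made because the error is clear and the display is one that the protocol requires.

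**What to change.** 1. When the onset month is the procedure month, impute a missing day as the later of the 1st of the month and the index procedure date, unless the case report form shows onset before the procedure. State whether imputed dates decide entry to the overall adverse event summaries.
2. In Table 2, define peri-procedure as the start of the procedure to 24 hours after guiding-catheter removal, using onset time where it is recorded. Where it is not, show Day 1 events in their own row, with a note that some may lie beyond 24 hours. A Day 0–1 label is the simpler alternative, but it takes in the extra hours shown in the first table above.
3. In SAP 10.4.4, change the gloss to after Day 450.

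The cost is a few lines of SAP text and program code. The documents do not say whether onset time is collected, so check that before choosing between the options in item 2.

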**e) Bleeding Complications:**

The number and percentage of subjects who experience a procedure-related hemorrhagic event which requires any of the following will be evaluated: blood transfusion, surgical intervention, a new hospitalization, or lengthening of hospital stay. The complications of hematoma requiring treatment (i.e., a hematoma > 5 cm in diameter occurring at the access site) and retroperitoneal bleeding will be reported as hemorrhagic events.

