## **HEMMORHAGE**

Acute loss of blood requiring transfusion

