### **VASCULAR COMPLICATIONS**

Vascular complication may include the following:

- Hematoma at access site > 4 cm
- Pseudoaneurysm
- Arteriovenous fistula
- Retroperitoneal bleed
- Peripheral ischemia/nerve injury
- Procedure related transfusion
- Vascular surgical repair

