5.2.2 Secondary Safety Endpoints

- Rate of new neurological deficits as per the modified Rankin Scale (mRS)

New neurological deficits will be evaluated in terms of mRS scores at baseline (pre-procedure) and follow-up (30 days, 6-Month and 12-Months post-procedure).

- NIH Stroke Scale (NIHSS) total score

Neurological morbidity will be assessed using the NIHSS total score. The NIHSS, administered by the investigator, is a 15-item scale used to evaluate the effect of acute cerebral infarction on the levels of consciousness, language, neglect, visual-field loss, extraocular movement, motor strength, ataxia, dysarthria, and sensory loss. A trained observer rates the subject's ability to answer questions and perform activities. Ratings for each item are scored on either zero to three or zero to five (with 0 as normal).

- Adverse events (AEs) and clinical complications

AEs including complications associated with an untoward medical occurrence, from the start of the index procedure until completion of the 12-Month Follow-up will be evaluated, including serious adverse events (SAEs), device- or procedure-related AEs, unanticipated adverse device effects (UADEs) and deaths.

- Reduced TICI flow

The percentage of target aneurysms in which a new occurrence of unintentional and persistent reduced TICI flow (TICI score of 0 or 1) is observed at the target vessel during the index procedure as a result of a mechanical obstruction such as dissection or luminal thrombus will be evaluated.

- Bleeding complications

The number and percentage of subjects who experience a procedure related hemorrhagic event which requires any of the following will be evaluated: blood transfusion, surgical intervention, a new hospitalization, or lengthening of hospital stay. The complications of hematoma requiring treatment (i.e., a hematoma > 5 cm in diameter occurring at the access site) and retroperitoneal bleeding will be reported as hemorrhagic events.

- In-stent stenosis

The percentage of aneurysms in which in-stent stenosis is documented immediately post-procedure (acute) and up to and including 6 months post-procedure, will be evaluated.

Acute in-stent stenosis will be further characterized by whether it results from vasospasm, and whether the vasospasm was responsive to medication.

- Thrombosis

The percentage of aneurysms in which thrombosis is documented up to and including 6 and 12 months post-procedure will be evaluated. Thrombosis is defined as in-stent thrombosis.

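### SAP 10.4.2.2 words the bleeding-complication count more narrowly than the endpoint in SAP 5.2.2 and the protocol, so the descriptive rate could be slightly too low

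*SAP*

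**What the plan says.** **Protocol.** The Overview (Secondary Safety Endpoints, item e), section 3.2.4.5 and section 9.6 define the endpoint alike. A subject counts if a procedure-related hemorrhagic event requires "blood transfusion, surgical intervention, a new hospitalization, or lengthening of hospital stay". Each place then adds that treated access-site hematoma over 5 cm and retroperitoneal bleeding are reported as hemorrhagic events. Appendix 1 has its own entry for Bleeding Complication. It lists the same four consequences and says that these complications may include the hematoma or the retroperitoneal bleed.

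**SAP 5.2.2.** The SAP's definition repeats the protocol's. It names "hematoma requiring treatment (i.e., a hematoma > 5 cm in diameter occurring at the access site" and closes with "and retroperitoneal bleeding will be reported as hemorrhagic events".

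**SAP 10.4.2.2.** The analysis section opens the count with "The number and percentage of subjects who experience a procedure-related hemorrhagic event which requires any of the following will be summarized" and lists four items: transfusion, surgery, "New hospitalizations" and "Lengthening of hospital stay for the index procedure". The item printed after these, in-stent stenosis, is the next endpoint. There is no mention of hematoma or retroperitoneal bleeding and no reference back to 5.2.2.

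**The concern.** The SAP describes one safety endpoint in two places that do not agree, and gives no rule for which prevails. The section a programmer is most likely to work from is the narrower one. Measured against 5.2.2, both differences can remove events and neither can add one.

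Bleeding is a harm worth counting consistently here. Protocol section 8 requires aspirin and a P2Y12 inhibitor before and after the procedure, and heparin during it. With hypothesis tests withdrawn (SAP sections 6 and 10.1), the reported percentage is itself the result. SAP 10.7 plans no sensitivity analyses. SAP section 11 puts the table shells in a separate document whose changes need no signature on the SAP, so the SAP text is the main signed control on what is counted.

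**Working it through.** The plan gives no rate, threshold or power for this endpoint, so there is no figure to reproduce. The check is a comparison of the wording.

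| Element | Protocol (Overview e, 3.2.4.5, 9.6) | Appendix 1, Bleeding Complication | SAP 5.2.2 | SAP 10.4.2.2 |
|---|---|---|---|---|
| Transfusion | yes | yes | yes | yes |
| Surgery | yes | yes | yes | yes |
| New hospitalization | yes | yes | yes | yes |
| Lengthened stay | any | any | any | index procedure only |
| Hematoma over 5 cm, retroperitoneal bleed | reported as hemorrhagic events | may be included | reported as hemorrhagic events | not mentioned |

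**Difference 1, the stay.** The limit to the index procedure appears only in SAP 10.4.2.2, and no reason is given.

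- A bleed that causes a readmission still counts, under "New hospitalizations".
- A bleed that prolongs the index stay still counts.
- What is left is a procedure-related bleed whose sole consequence is to lengthen some other admission. One route is a bleed at a later procedure on the aneurysm that prolongs that admission. Protocol section 6.2.4 applies the procedure assessments to subsequent procedures as well as the index one, so such a bleed would be recorded. Whether it is procedure-related for this endpoint is not spelled out.
- Such a bleed meets the SAP 5.2.2 wording and fails the 10.4.2.2 wording.

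**Difference 2, hematoma and retroperitoneal bleeding.** The sentence in SAP 5.2.2 can be read in two ways.

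- *Reading A:* these bleeds count on their own. A 6 cm groin hematoma treated locally, with discharge on time, is then in the endpoint under 5.2.2 and outside the 10.4.2.2 list. The separate threshold in the hematoma clause (treated, over 5 cm) favours this reading, since it would do little if one of the four consequences were still needed.
- *Reading B:* these bleeds are classed as hemorrhagic events and must still have one of the four consequences. The permissive wording in Appendix 1 fits this. On this reading the omission loses nothing.

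The documents do not settle which is meant.

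**Size.** Let k be the number of subjects with an event under 5.2.2, m the number of those who qualify only through a component absent from 10.4.2.2, and N the denominator.

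- Rate under 5.2.2: k/N
- Rate under 10.4.2.2: (k − m)/N
- Shortfall: k/N − (k − m)/N = m/N, which is 100/N percentage points per missed subject

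None of k, m or N is given. SAP section 8 bases the analysis on the enrollment actually achieved, so neither the planned 160 nor the planned 320 can stand in for N. SAP 10.1 further bases percentages on non-missing values. A smaller N makes each missed subject weigh more.

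**The case against.** **Section 5 defines and section 10 abbreviates.** This is the strongest reply. The reduced-TICI entry in SAP 10.4.2.2 also leaves out qualifiers stated in 5.2.2 (new, unintentional and persistent, mechanical cause), and SAP 10.4.2.1 does not restate the definition of procedure success. Not repeating a definition is not the same as deleting it. This stands for the hematoma and retroperitoneal sentence: 5.2.2 keeps both bleed types in the SAP. It does not cover the stay criterion, where 10.4.2.2 adds a restriction.

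**Lengthened stay may always have meant the index stay.** Set beside a new hospitalization, it can be read as the contrast between a readmission and the index stay. That is possible, but only 10.4.2.2 says so. If it was intended, the definition should say it too.

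**The bleeds stay visible.** SAP 10.4.2.2 tabulates all adverse events, device- or procedure-related events and serious events by system organ class and preferred term. This stands. It limits the harm but does not correct the bleeding rate.

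**Stronger readings that the documents do not support.**

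- A reader might infer that the Appendix 1 entry for hemorrhage, "Acute loss of blood requiring transfusion", makes the other three consequences redundant. The same appendix has a specific entry for Bleeding Complication, which accepts all four and is the natural governing definition.
- A reader might see a conflict in "Hematoma at access site > 4 cm". That limit belongs to the entry for vascular complications, a different term that this endpoint does not use.
- A reader might think that an intracranial bleed that prolongs the index stay without transfusion is lost. SAP 10.4.2.2 counts it as a lengthened index stay.
- A reader might conclude that qualifying bleeds will drop out of the rate. That is a risk under particular readings, not an established result.

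**Conclusion.** The mismatch is real and minor. SAP 10.4.2.2 does not reproduce the endpoint defined in SAP 5.2.2 and the protocol.

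- Taken literally, it excludes a procedure-related bleed whose only consequence is a longer stay other than the index stay. This assumes that the unrestricted wording of 5.2.2 and the protocol is the intended endpoint.
- It also excludes treated hematomas over 5 cm and retroperitoneal bleeds with none of the four consequences, but only if those bleeds are meant to count on their own.

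Either loss would make the descriptive rate slightly too low, by 100/N percentage points per subject. The total cannot be estimated from the documents. The endpoint is secondary, has no performance goal and is reported descriptively in a study that is stopping early, so no decision rule is affected.

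**What to change.** In SAP 10.4.2.2:

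1. Delete the limit to the index procedure from the stay criterion.
2. State that the SAP 5.2.2 definition applies, including its sentence on hematoma and retroperitoneal bleeding.
3. Report treated access-site hematoma over 5 cm and retroperitoneal bleeding in the bleeding table. Those that meet none of the four consequences go on a separate line if they are not meant to count on their own. This keeps them visible without widening the protocol endpoint.

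Optionally, note that the Bleeding Complication entry in Appendix 1 governs this endpoint. No other change to the appendix is needed for this point.

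The cost is a few lines of SAP text and a matching change to one table shell. The reported bleeding rate may come out slightly less favourable.
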